4.1 GENERAL CONSIDERATIONS

Unless otherwise specified, all data will be summarized for each age cohort (<6 years and 6 to <12 years) and overall.

The surgery subgroup will be included in baseline tables as well as the overall AE summary. When the surgery subgroup is included in a summary table, participants who participated in the surgery subgroup will be included in the columns for age cohort and the surgery subgroup but will only be counted once in the overall column.

Baseline

Baseline is defined as the last non-missing measurement taken prior to the first dose of study drug, excluding measurements taken during a surgical/rehabilitation period. For HJHS, if there are no measurements taken prior to the first dose of the drug, and the first measurement is taken no more than 7 days after the first dosing, then this first measurement will be considered as baseline for HJHS.

Study Day

Study day is defined as the number of days relative to the date of the first dose of study drug. The first dose of study drug is Day 1. Study day will be calculated as (date of event – first dose date +1) if the date of event is on or after the first dose date or (date of event – first dose date) if the date of event is before the first dose date. If the date of event is missing or partial, the corresponding study day will be left blank.

Exposure Day

One exposure day (ED) is defined as a 24-hour period in which a participant receives 1 or more doses of study drug, with the time of the first injection of study drug defined as start of the ED.

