4.6 MULTIPLICITY ISSUES

All analyses are descriptive in nature and therefore adjustments for multiplicity will not be applied.

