When injections are identified in the ePD with exactly the same date/times, bleed information if applicable (type, location, and sublocation), lot numbers, number of vials, and vials strength in nominal IU, these may have resulted due to administrative issues and are therefore true duplicates. There are three types of administrative issues as follows:

- Technical transmission issue
- Entry of same record into 2 different devices
- Records duplicated in ePD and eCRF which remain despite attempts to correct the data via the query process

The programming algorithm to identify and delete the duplicates is as follows:

- Identify all injections that have exactly the same date/times, reasons for injection, bleed information (if applicable), lot numbers, number of vials, and vials strength in nominal IU
- Remove the duplicates and keep a single record

As with single vial consolidation, if injections identified as duplicates have distinctly different reasons (eg, one injection is recorded as bleeding or surgery and another is recorded as prophylaxis or OTHER), then these cannot be considered duplicates and removed. However, if one reason is missing, then they can be considered duplicates and removed.

Algorithm for determining analysis visit windows for PRO and HJHS observations

A scheduled measurement will be used if it is available. Otherwise, the following analysis window will decide how the unscheduled and EOS/ET visits will be used in the analyses of PRO and HJHS variables.

A measurement (unscheduled or EOS/ET) will be used if it is available and measurement date is within the analysis window.

After applying these time windows, if multiple assessments are associated to the same time point, the closest from the targeted study day will be used. If the difference is a tie, the value after the targeted study day will be used. If multiple valid values exist within a same day, then the first value of the day will be selected.

Scheduled visit post		Derived Window in study days		
baseline	Target study day	Lower bound	Upper bound	
Baseline	1	-INF	1(7 for HJHS)	
Week 26	182	2 (8 for HJHS)	272	
Week 52	364	273	-	

Table 6 - Analyses window definition

Handling of adverse events with missing or partial date/time of onset

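### SAP Table 6 lets an early-termination PRO or HJHS value from the first days of treatment count as Week 26, and its HJHS baseline window disagrees with SAP 4.1

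*SAP*

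**What the plan says.** SAP Appendix 3 (5.3) gives precedence to planned visits: "A scheduled measurement will be used if it is available". Failing that, "the following analysis window will decide how the unscheduled and EOS/ET visits will be used in the analyses of PRO and HJHS variables". The rule for use is: "A measurement (unscheduled or EOS/ET) will be used if it is available and measurement date is within the analysis window". If several values compete, "if multiple assessments are associated to the same time point, the closest from the targeted study day will be used", and a tie goes to the value after the target day.

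Table 6, under "Derived Window in study days", sets:

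| Visit | Target day | Lower bound | Upper bound |
|---|---|---|---|
| Baseline | 1 | none (-INF) | 1 (7 for HJHS) |
| Week 26 | 182 | 2 (8 for HJHS) | 272 |
| Week 52 | 364 | 273 | none |

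SAP 4.1 has its own baseline rule: "Baseline is defined as the last non-missing measurement taken prior to the first dose of study drug". For HJHS alone, when there is no pre-dose value, the first post-dose value serves as baseline if "the first measurement is taken no more than 7 days after the first dosing". The same section numbers the day of first dose as Day 1.

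In the protocol, HJHS, Haemo-QoL, PROMIS and EQ-5D-Y are scheduled at Baseline, Week 26 and Week 52. EOS/ET shares the Week 52 column of protocol Table 1, and the visit tolerance is ±7 days.

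**The concern.** A child who leaves before Week 26 and is not followed further has no scheduled Week 26 value, so precedence for scheduled values does not protect that visit. The EOS/ET value fills it, and the closest-to-target rule does nothing when there is only one candidate. Protocol 7.1.1 and 7.2 ask for the EOS/ET assessments at discontinuation. Protocol 4.4 also calls in every ongoing participant once the study milestones are met, whatever study day they have reached. Early EOS/ET values are therefore foreseen by the design. A reader of the Week 26 table would take them for changes after about half a year of prophylaxis.

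The HJHS conflict is of another kind: two sections of the SAP can classify one measurement differently. If Day 8 is not baseline, the child has no baseline and no change score at any visit.

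**Working it through.** **Inputs.** Targets (Days 1, 182, 364) and bounds are from SAP Table 6. Study day on or after first dose is event date minus first-dose date plus 1 (SAP 4.1). The ±7-day tolerance is from protocol Table 1.

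**1. Reproduce the upper cut.** Midpoint of Week 26 and Week 52: (182 + 364)/2 = 273. The 272/273 split in Table 6 follows the midpoint rule.

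**2. Apply the same rule below.** Midpoint of Baseline and Week 26: (1 + 182)/2 = 91.5, so Week 26 would start at Day 92. Table 6 instead takes the baseline bound plus one: 1 + 1 = 2 for PRO and 7 + 1 = 8 for HJHS.

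**3. Resulting shape.**
- PRO: 272 − 2 + 1 = 271 days, reaching 182 − 2 = 180 days before target and 272 − 182 = 90 days after.
- HJHS: 272 − 8 + 1 = 265 days, reaching 182 − 8 = 174 days before and 90 after.
- Midpoint on both sides: Days 92 to 272, which is 90 days each way.
- Protocol visit tolerance: 182 ± 7, or Days 175 to 189.

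**4. Labels for an EOS/ET value when the scheduled value is absent** (weeks = (day − 1)/7):

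| Study day | Weeks since first dose | PRO, Table 6 | HJHS, Table 6 | Midpoint rule for Week 26 |
|---|---|---|---|---|
| 2 | 0.1 | Week 26 | Baseline | outside |
| 8 | 1.0 | Week 26 | Week 26 | outside |
| 30 | 4.1 | Week 26 | Week 26 | outside |
| 91 | 12.9 | Week 26 | Week 26 | outside |
| 92 | 13.0 | Week 26 | Week 26 | inside |
| 272 | 38.7 | Week 26 | Week 26 | inside |
| 273 | 38.9 | Week 52 | Week 52 | Week 52 |

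**5. HJHS baseline, first conflict.** Seven days after first dosing is study day 7 + 1 = 8. Under SAP 4.1 a first HJHS on that day, with nothing before the dose, is baseline. Under Table 6 the baseline window closed on Day 7, and Day 8 belongs to Week 26.

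**6. HJHS baseline, second conflict.** Table 6 does not carry over the condition that no pre-dose value exists. Suppose unscheduled HJHS values on Day −10 and Day 5, with no scheduled baseline. SAP 4.1 selects Day −10. Table 6 selects Day 5, since 5 − 1 = 4 days from target is less than the 10 days (11 by plain subtraction, as the SAP has no Day 0) for Day −10.

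**The case against.** The strongest case is that little depends on this. The HJHS and Haemo-QoL secondary endpoints are changes to Week 52, so the lower bound touches only an intermediate summary. SAP 4.6 states: "All analyses are descriptive in nature and therefore adjustments for multiplicity will not be applied". The inhibitor endpoint and ABR do not use these windows. Protocol Table 1 schedules none of these instruments at unscheduled visits, so in practice the matter concerns EOS/ET visits. Protocol 7.1.1 provides for follow-up after stopping drug, so some children who stop early may still have a scheduled Week 26 value. Contiguous windows that keep every post-baseline value are also a legitimate pre-specified choice, because dropping early leavers shifts the summary toward those who stayed. All of this stands and limits the point. It does not make a value at one or four weeks a 26-week value.

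Readers might infer more than the documents support:
- **That Week 52 starting at Day 273 is also wrong.** It is an ordinary midpoint. The open upper bound has little practical reach, since the only contact after the final visit is a safety call or visit with no HJHS or PRO scheduled.
- **That 15 of 65 children (23%) will supply early values.** That is the gap between approximate enrollment and the minimum number reaching 50 exposure days, not a forecast of early termination.
- **That the Week 26 change is pulled toward zero.** Children who leave because of adverse events or poor control could score worse, so the direction is not established.
- **That Day 8 is a likely catch-up day for HJHS because PK children attend then.** Protocol Table 2 lists only FVIII activity sampling on that day.

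**Conclusion.** Both parts hold, within limits. The Week 26 window departs from the midpoint rule that fixes its own upper edge, so EOS/ET values from Day 2 (Day 8 for HJHS) to Day 91 would be summarized as Week 26 when no scheduled value exists. The effect is confined to the descriptive Week 26 summary. Separately, Table 6 and SAP 4.1 disagree on HJHS baseline. That could change or remove the Week 52 HJHS change, a secondary endpoint, for a child whose first HJHS falls on Day 8.

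The number of affected values cannot be computed, because the documents give no count of early EOS/ET assessments or late first HJHS assessments. The Day 8 conflict assumes the SAP's day numbering taken literally and a value not recorded as the scheduled baseline. If 7 days after dosing is read loosely as Day 7, that conflict disappears, but the missing no-pre-dose condition remains. The point deserves correction before database lock and does not threaten the trial's main results.

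**What to change.** Amend SAP Table 6 in three respects:

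1. Start the Week 26 window at Day 92 for PRO and HJHS, keeping Day 272 as its end and leaving the Week 52 row unchanged.
2. List unscheduled and EOS/ET values taken after the baseline window and before Day 92, without including them in the by-visit summary.
3. Set the HJHS baseline upper bound to Day 8, and state in the table that a post-dose value qualifies only when there is no pre-dose HJHS, as in SAP 4.1.

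The cost is an edit to one table and its programming, with no change to data collection. The downside is that a few very early EOS/ET values leave the Week 26 summary, which then represents more closely the children who stayed on study. Those values remain visible in the listing.

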5.4 APPENDIX 4 POTENTIALLY CLINICALLY SIGNIFICANT ABNORMALITIES CRITERIA

Parameter name	Age	Low	High
White Blood Cells	6 to <12 years old	<5.0 Giga/L or 5,000/mm ³	>17.0 Giga/L or 17 000/mm ³
	24 months/2 years to <6 years old	<3.0 Giga/L or 3,000/mm ³	>16.0 Giga/L or 16 000/mm ³
	28 days/1 month to 23 months old	<4.0 Giga/L or 4000/mm ³	>20.0 Giga/L or 20 000/mm ³
	Birth/0 to 27 days old	<4.0 Giga/L or 4000/mm ³	>25.0 Giga/L or 25 000/mm ³
Neutrophils	6 to <12 years old	<1.2 Giga/L or 1200/mm ³	>1 ULN
	24 months/2 years to <6 years old	<1.2 Giga/L or 1200/mm ³	>1 ULN
	28 days/1 month to 23 months old	<1.0 Giga/L or 1000/mm ³ (1-3 months)	>1 ULN
		<1.2 Giga/L or 1200/mm ³ (3-24 months)	
	Birth/0 to 27 days old	<4.0 Giga/L or 4000/mm ³ (1 day old)	>1 ULN
		<1.5 Giga/L or 1500/mm³ (2-7 days old)	
		<1.25 Giga/L or 1250/mm ³ (>7 day-1 month old)	
Lymphocytes	6 to <12 years old	<1.0 Giga/L or 1000/mm ³	>8.0 Giga/L or 8000/mm ³
	24 months/2 years to <6 years old	<1.0 Giga/L or 1000/mm ³	>9.5 Giga/L or 9500/mm ³
	28 days/1 month to 23 months old	<2.0 Giga/L or 2000/mm ³	>13.5 Giga/L or 13 500/mm ³
	Birth/0 to 27 days old	<1.2 Giga/L or 1200/mm ³	>17.0 Giga/L or 17 000/mm³
Hemoglobin	24 months/2 years to <12 years old	<1.55 mmol/L or 10.0 g/dL or any decrease	> 0.31 mmol/L or 2 g/dL
	28 days/1 month to 23 months old	<1.40 mmol/L or 9.0 g/dL or any decrease	> 0.31 mmol/L or 2 g/dL

 Table 7 - Threshold levels for potentially clinically significant hematology abnormalities

Parameter name	Age	Low	High	
	Birth/0 to 27 days old	<8.6 mmol/L or 12.0 g/dL or any decrease	≥0.31 mmol/L or 2 g/dL	
Hematocrit	24 months/2 years to <12 years old	<0.32 l/l or 32%	>0.47 l/l or 47%	
	28 days/1 month to 23 months old	<0.29 l/l or 29%	>0.42 l/l or 42%	
	Birth/0 to 27 days old	<0.39 l/l or 40%	>0.61 l/l or 47%	
Platelet count	<12 years	<100 Giga/L or 100 000/mm ³	>700 Giga/L or 700 000/mm ³	

N/A = not applicable

Table 8 - Threshold levels for potentially clinically significant chemistry abnormalities

Parameter name	Age	PCS low	PCS high
Sodium	<12 years	≤129 mmol/L or 129mEq/L	≥150 mmol/L or 150mEq/L
Potassium	24 months/2 years to <12 years old	≤3.5 mmol/L or 3.5 mEq/L	≥5.5 mmol/L or 5.5 mEq/L
	28 days/1 month to 23 months old	≤3.5 mmol/L or 3.5 mEq/L	≥6.0 mmol/L or 6.0 mEq/L
	Birth/0 to 27 days old	≤3.0 mmol/L or 3.0 mEq/L	≥7.0 mmol/L or 7.0 mEq/L
Chloride	<12 years	≤80 mmol/L or 80mEq/L	≥115 mmol/L or 115 mEq/L
ALT/SGPT	<12 years	N/A	≥3 x ULN

	24 months/2 years to <6 years old	≤34 mmHg and decrease from baseline ≥10 mmHg	≥59 mmHg and increase from baseline ≥10 mmHg
	28 days/1 month to 23 months old	≤34 mmHg and decrease from baseline ≥10 mmHg	≥54 mmHg and increase from baseline ≥10 mmHg
	Birth/0 to 27 days old	≤34 mmHg and decrease from baseline ≥10 mmHg	≥50 mmHg and increase from baseline ≥10 mmHg
Orthostatic hypotension	< 12 years	SBP : St - Su ≤-20 mmHg DBP : St - Su ≤-10 mmHg	N/A
Sa02	<12 years	≤95%	N/A
Weight	<12 years	N/A	≥5% weight loss from baseline
Heart Rate	6 to <12 years old	≤50 bpm and decrease from baseline ≥20 bpm	≥120 bpm and increase from baseline ≥20 bpm

Variable	Age	Low	High
	24 months/2 years to <6 years old	≤75 bpm and decrease from baseline ≥20 bpm	≥140 bpm and increase from baseline ≥20 bpm
	28 days/1 month to 23 months old	≤80 bpm and decrease from baseline ≥20 bpm	≥175 bpm and increase from baseline ≥20 bpm
	Birth/0 to 27 days old	≤90 bpm and decrease from baseline ≥20 bpm	≥190 bpm and increase from baseline ≥20 bpm
Temperature	<12 years	N/A	Ear/temporal artery: ≥100.4°F/38.0°C Oral: ≥99.5°F/37.5°C Axillary: ≥99°F/37.2°C
Respiration Rate	6 to <12 years old	<18 per minute	>30 per minute
	24 months/2 years to <6 years old	<22 per minute	>34 per minute
	28 days/1 month to 23 months old	<24 per minute	>40 per minute
	Birth/0 to 27 days old	<30 per minute	>60 per minute

5.5 APPENDIX 5 QUESTIONNAIRE SCORING

5.5.1 Appendix 5.1 PROMIS instruments

Six PROMIS instruments are used in this study:

- a) PROMIS Pediatric NRS Pain Intensity (v1.0 Pain Intensity 1a; \geq 8 years old)
- b) PROMIS Parent Proxy NRS Pain Intensity (v1.0 Pain Intensity 6b; 5 to <12 years old)
- c) PROMIS Pediatric-SF Pain Interference (v2.0 Pain Interference $8a; \ge 8$ years old)
- d) PROMIS Parent Proxy-SF Pain Interference (v2.0 Pain Interference 8a; 5 to <12 years old)
- e) PROMIS Pediatric-SF Physical Activity (v1.0 Physical Activity 8a; \geq 8 years old)
- PROMIS Parent Proxy-SF Physical Activity (v1.0 Physical Activity 8a; 5 to <12 years old)

For PROMIS instruments c) - f), within each instrument, each question has five response options ranging in value from one to five. To find the total raw score for an instrument with all questions answered, sum the values of the response to each question. All questions must be answered in order to produce a valid total score. For pain intensity forms, the items are not calibrated and do not produce a T-score. Instead, raw response scores (0 to 10) should be used for analyses. For other forms, total raw score is then converted into a T-score for each participant using an instrument-specific *Conversion Table* as provided in Table 11. The T-score rescales the raw score into a standardized score with a mean of 50 and a standard deviation (SD) of 10. Therefore, a person with a T-score of 40 is one SD below the mean.

(c) PROMI Interferend					S Pediatri ctivity (≥8				S-SF Pain ce (5 to <12	2 years)
	Interferenc ediatric v2.				ical Activity ediatric v1.			Pain Inte	rference 8a Proxy v2.0	- Parent
	rm Conversi	-			rm Conversi		1 1	Short Fo	rm Conversi	on Table
Raw Score	T-Score	SE*		Raw Score	T-Score	SE*		Raw Score	T-Score	SE*
8	34.0	5.6		8	28.8	4.8	1 1	8	38.0	6.0
9	38.7	4.4		9	32.6	3.8	1 [9	44.0	3.0
10	40.6	4.2		10	34.5	3.5	1 [10	46.0	3.0
11	42.7	3.8		11	36.4	3.1	1 [11	48.0	3.0
12	44.3	3.7		12	37.9	2.8	1 [12	49.0	2.0
13	45.8	3.4		13	39.2	2.6	1 [13	50.0	2.0
14	47.1	3.3		14	40.4	2.5	1 [14	51.0	2.0
15	48.4	3.2		15	41.4	2.4	1 [15	52.0	2.0
16	49.5	3.2		16	42.4	2.3	1 [16	53.0	2.0
17	50.6	3.1		17	43.4	2.3	1 [17	54.0	2.0
18	51.7	3.1		18	44.3	2.3	1 [18	55.0	2.0
19	52.7	3.1		19	45.2	2.3	1	19	56.0	2.0
20	53.7	3.0		20	46.1	2.3	1 [20	57.0	2.0
20	54.7	3.0		21	47.0	2.3	1 [21	58.0	2.0
22	55.7	3.0		22	47.8	2.3	1	22	58.0	2.0
23	56.6	3.0		23	48.7	2.3	1	23	59.0	2.0
23	57.6	3.0		24	49.6	2.3	1	24	60.0	2.0
24	58.5	3.0		25	50.5	2.3	1	25	61.0	2.0
		3.0		26	51.4	2.3	1	26	62.0	2.0
26	59.5	3.0		27	52.3	2.4	1	27	62.0	2.0
27	60.4	3.0		28	53.3	2.4		28	63.0	2.0
28	61.4	3.0		29	54.3	2.4	1	29	64.0	2.0
29	62.4	3.0		30	55.3	2.4	1	30	65.0	2.0
30	63.4	3.0		31	56.3	2.4	1	31	66.0	2.0
31	64.4			32	57.3	2.4	1	32	67.0	2.0
32	65.4	3.1		33	58.4	2.4	$\frac{1}{2}$	33	67.0	2.0
33	66.5	3.1		34	59.5	2.5	$\frac{1}{2}$	34	68.0	2.0
34	67.6	3.2		35	60.8	2.5	$\frac{1}{2}$	35	69.0	2.0
35	68.8	3.2		36	62.1	2.5	$\frac{1}{2}$	36	70.0	2.0
36	70.1	3.3	\vdash					37	71.0	3.0
37	71.5	3.4	\vdash	37	63.7	2.8		38	73.0	3.0
38	73.2	3.7	\vdash	38	65.5	3.1	[39	74.0	3.0
39	75.0	3.8	\vdash	39	67.8	3.5	4 [40	78.0	4.0
40	78.0	4.3	**	40	71.7 deed Error (4.6	J	*SE = Stan	dard Error o	on T-Score
*SE = Stan	dard Error o	on T-Score	-5	c = stan	dard Error o	on 1-Score			on default P	

Table 11 - Conversion table for PROMIS instruments

(f) PROMIS Parent Proxy-SF Physical Activity (5 to <12 years)

Physical Activity 8a - Parent					
Proxy v1.0					
Short Fo	rm Convers	ion Table			
Raw	T-Score	SE*			
Score					
8	28.4	4.9			
9	31.9	4.0			
10	33.5	3.7			
11	35.5	3.3			
12	37.0	3.0			
13	38.4	2.8			
14	39.6	2.7			
15	40.7	2.6			
16	41.8	2.5			
17	42.8	2.5			
18	43.8	2.5			
19	44.7	2.5			
20	45.7	2.5			
21	46.6	2.5			
22	47.6	2.6			
23	48.6	2.6			
24	49.6	2.6			
25	50.6	2.6			
26	51.6	2.6			
27	52.6	2.6			
28	53.7	2.6			
29	54.8	2.6			
30	55.9	2.6			
31	57.1	2.6			
32	58.3	2.7			
33	59.5	2.7			
34	60.9	2.7			
35	62.3	2.8			
36	63.8	2.9			
37	65.5	3.0			
38	67.5	3.3			
39	70.0	3.7			
40	73.7	4.6			

5.5.2 Appendix 5.2 Haemo-Qol

The Haemo-Qol questionnaires for children aged 4-7 years will be summarized in terms of a total score, and the questionnaires for children aged 8 to <12 years will be summarized in terms of subscale scores and a total score according to the recommendations of the questionnaire authors.

When missing data are presented, a subscale/total score can only be calculated if at least 50% of questions for that subscale/questionnaire are answered (non-missing and not "Not Applicable").

Haemo-QoL (age group I; 4-7 years old)

The Haemo-Qol questionnaire for participants with hemophilia who are 4-7 years of age consists of 16 items for past 4 weeks time period.

Haemo-QoL (age group II; 8 to <12 years old)

The Haemo-Qol questionnaire for participants with hemophilia who are 8-<12 years of age consists of 35 items pertaining to 9 subscales for past 4 weeks time period.

Time Period	Subscales for Haemo-QoL	No. of questions	No. of non-missing items required to calculate subscale
In the past 4 weeks	1. Physical health	4	2
	2. Feeling	4	2
	3. View of yourself	4	2
	4. Family	4	2
	5. Friends	3	2
	6. Other persons	4	2
	7. Sports and school	4	2
	8. Dealing with hemophilia	4	2
	9. Treatment	4	2
	Total Score	35	18

Haemo-QoL parent proxy (age group I; 4-7 years)

The Haemo-QoL questionnaire for parents of participants with hemophilia who are 4-7 years of age consists of 16 items for past 4 weeks time period.

Haemo-QoL parent proxy (age group II; 8 to <12 years)

The Haemo-QoL questionnaire for parents of participants with hemophilia who are 8 to <12 years of age consists of 35 items pertaining to 9 subscales for past 4 weeks time period.

Time Period	Subscales for Haem-A-QoL	No. of questions	No. of non-missing items required to calculate subscale
In the past 4 weeks	1. Physical health	4	2
	2. Feeling	4	2
	3. View of yourself	4	2
	4. Family	4	2
	5. Friends	3	2
	6. Other persons	4	2
	7. Sports and school	4	2
	8. Dealing with hemophilia	4	2
	9. Treatment	4	2
	Total Score	35	18

Scoring algorithm

Per the algorithm on http://www.haemoqol.de/manual.htm, to correctly score the questionnaires, each version has to be identified and the appropriate scoring list has to be selected. High score represent low quality of life and scoring involves the following steps:

1. Assigning numbers to the response scale

```
1= never, 2=seldom, 3=sometimes, 4=often, 5=always
```

For negatively worded items, the above classification can be applied in which higher values represent a lower quality of life. For positively worded items, the score has to be recoded (see below).

2. Recoding positively worded items

Positively worded items in table have to be recoded so that numeric values assigned are reversed:

```
1=always, 2=often, 3=sometimes, 4=seldom, 5= never
```

By recoding, high scores in positively worded items reflect not higher but lower quality of life. The then unidirectional values can subsequently be added to yield the summed scores according to the scoring list.

3. Producing the raw score

A raw subscale score is produced by summing up all items within a subscale. Its range lies between the lowest possible (number of items $(n) \ge 1$) and highest possible (number of items $(n) \ge 5$) value of the respective scale.

The raw total score is produced by the addition of all items (instead of the subscale items only) of the questionnaire (again paying attention to the recoding procedure - see Steps 1 and 2).

4. Transferring a raw score to a Transformed Scale Score (TSS) between 0 and 100

Creating a Transformed Scale Score (TSS) makes it possible to express the score as a percentage between the lowest (0) and the highest (100) possible value. To obtain the TSS the following transformation rule has to be applied:

TSS = 100 x ((raw score – minimal possible raw score) / possible range of raw scores) where:

- minimal possible raw score = number of questions answered $\times 1$
- maximal possible raw score = number of questions answered $\times 5$
- possible range of raw scores = maximum possible raw score minimal possible raw score

Example: A raw score of 12 on the "Physical Health" scale is to be transformed:

- When all 4 questions were answered:
 - minimal possible score=4
 - maximal possible score=20
 - range of scores=16
 - TSS = (12-4)/16 = 50
- When 3 of the 4 questions were answered:
 - minimal possible score=3
 - maximal possible score=15
 - range of scores=12
 - TSS = (12-3)/12 = 75

Transformed scores can be produced from raw subscale and raw total scores.

The total and subscale scores based on TSS will be presented in outputs.

6 **REFERENCES**

